9.3. Concomitant Medication

A concomitant medication is any medication that starts prior to first day of study drug administration and continues into treatment period, or started after the first dose of IMP. In the case of completely missing stop date and medication is not ongoing, medication will be assumed to be concomitant.

Concomitant medication summaries based on ATC level 3 and the preferred drug names will be produced for the Safety Analysis Set. The summaries will present, the frequency and percentage of patients who used any medication in an ATC class, or any medication based on a single preferred drug name. Medication summaries will be sorted by descending total frequency of ATC class and by PT within ATC class. Patients will be counted only once for each medication class and each preferred drug name. Concomitant medication will be summarized for entire treatment period in one overall column. No by age group summary will be included.

In addition, ADHD and antidepressant medication(see Section 7.4.1 for ATC code list) change will be summarized for:

- Proportion of patients with requiring increased medication;
- Proportion of patients requiring decreased/stopped medication;

Proportion of patients with medication switch. The proportion of patients who alter their medication. A separate listings will be provided for these patients with all ADHD and antidepressant medications.

All summary tables will be presented for Parts I and III combined, and Part II.

This document is confidential.

9.4. Adverse Events

Adverse events will be collected and recorded from the time a patient signs the TV50717-CNS-30047 informed consent to the end of follow-up period.

For all AEs, preferred AE terms and system organ class (SOC) will be coded using terminology from the Medical Dictionary for Regulatory Activities (MedDRA), version 20.1.

A treatment emergent adverse event (TEAE) is defined as an AE that begins after the first administration of study medication or existing AEs that worsen after the first dose of study medication. All reported AEs will be listed, but only TEAEs will be summarized in tables.

Drug related AEs will be considered those to be reasonable possibility based on the investigators assessment. Missing relationship will be considered as "Related".

Unless otherwise specified, AEs will be summarized by SOC and PT, with SOC and PTs within SOC presented in descending order of patient incidence.

AE summary tables are listed below:

- An overall summary of the number and percentage of patients reporting any TEAEs, serious TEAEs, treatment-related TEAEs, serious treatment-related TEAE, any TEAEs leading to study drug discontinuation, any TEAEs leading to patient dose interruption, any TEAEs leading to patient dose reduction, and TEAEs leading to death. Same summaries will also be presented by each of the age group at entry into the parent study: 6- 11 years and 12- 16 years and parent study baseline CYP2D6 impairment status (Impaired/Not impaired).
- TEAEs overall and by SOC and PT;
- TEAEs by severity, overall and by SOC and PT. Missing severity, if any, will be assumed as "severe";
- Serious TEAEs, overall and by SOC and PT;
- Serious and related TEAEs, overall and by SOC and PT;
- TEAEs by relationship to study treatment, overall and by SOC and PT
- TEAEs leading to study drug discontinuation, overall and by SOC and PT;
- TEAEs leading to dose interruption, overall and by SOC and PT;
- TEAEs leading to dose reduction, overall and by SOC and PT;
- Most common TEAEs, overall and by PT. Most common TEAEs are defined as TEAEs that occur in > 4% of the patients;
- SMQs for suicide/self-injury and depression (exclude suicide and self-injury) and Parkinson-like events.

All AEs will be allocated to Parts (Section 6.2.6) or Periods (Section 6.2.7), depending on in which Part or Period the TEAEs occurs. Tables will be presented by Parts or Periods as below:

- Parts I and III combined, based on the Safety Analysis Set. The events that occurred in Part II will not be included. Table will contain one overall column. All tables will include number, frequency of patients with the event, and EAIR. All AE tables will be prepared for Part I and III combined.

This document is confidential.

Statistical Analysis Plan for Interventional Studies

Sponsor: Teva Branded Pharmaceutical Products R&D, Inc./Nuvelution TS Pharma, INC.
Protocol No.: TV50717-CNS-30047

- Part II is based on the RWSAF population and presented by the actual treatment received during the randomized withdrawal period. Table will include number and frequency of patients with the event. All AE tables will be prepared for Part II.
- Parts I, II, and III combined, based on the Safety Analysis Set. Table will contain one overall column. The Parts I, II, and III combined tables will be presented for entire study and by each Part. All tables will include number, frequency, and the EAIR. The overview of AEs, AEs by SOC and preferred terms, and the SMQ summaries will be presented for Parts I, II, and III combined.
- Periods, based on the Safety Analysis Set. Table will contain one overall column. All tables will include number, frequency, and the EAIR. The overview of AEs and AEs by SOC and preferred terms will be presented by periods.

For summary of patient, the following rules will apply:

1. Patients having more than 1 event with the same PT will be counted once for that term.
2. Patients having more than 1 event with the same SOC will be counted once for each event and once for that SOC.
3. For tabulations by severity, only a patient's most severe event within the category (e.g. overall, SOC, PT) will be counted; similarly, for tabulations by relationship, only a patient's most related event within a category will be counted. The denominator for percentages will be the number of patients in Safety Analysis Set for the given treatment group or overall (i.e., the N's for the columns).

For the summary of incidence rate, all events will be included.

Listings will be provided for all AEs and the following subsets:

- All TEAEs
- Serious TEAEs
- TEAEs leading to study drug discontinuation
- TEAEs leading to dose interruption
- TEAEs leading to dose reduction
- TEAEs leading to death.

9.5. Laboratory Evaluations

Laboratory tests will include chemistry panel, hematology panel, and urinalysis testing. Laboratory tests will be performed per [Table 3](#). A list of laboratory tests is included in [Table 6](#).

The observed values (in SI units) and the change from the Part I baseline to all post-baseline visits will be summarized. For hematology and chemistry panel, result will also be categorized as "Normal", "Low", or "High" based on their normal ranges. For urinalysis results, tests will be classified as "Normal" or "Abnormal". Shift tables comparing laboratory test results from baseline to each post-baseline visits will be presented.

All laboratory data will be listed. For hematology, chemistry, columns will be included for normal ranges and individual abnormal laboratory values will be flagged. Listing for urinalysis will include the microscopic examination provided for patients who have a positive result from the urinalysis dipstick evaluation.

This document is confidential.

Table 6: List of Laboratory Tests

Serum Chemistry	Hematology	Urinalysis
calcium	hemoglobin	protein
phosphate	hematocrit	glucose
sodium	red blood cell (RBC) count	ketones
potassium	mean cell volume	blood (hemoglobin)
chloride	platelet count	pH
creatinine	white blood cell (WBC) count, and differential count	specific gravity
glucose	– absolute neutrophil count (ANC)	microscopic
magnesium	– polymorphonuclear leukocytes (neutrophils)	– bacteria
blood urea nitrogen (BUN)	– lymphocytes	– RBCs
total cholesterol	– eosinophils	– WBCs
uric acid	– monocytes	– casts
alanine aminotransferase (ALT)	– basophils	– crystals
aspartate aminotransferase (AST)		
lactate dehydrogenase (LDH)		
alkaline phosphatase (ALP)		
bicarbonate or carbon dioxide		
total protein		
albumin		
total bilirubin		
direct bilirubin		

9.6. Pregnancy

Human chorionic gonadotropin tests in urine or serum will be performed for all females who are postmenarchal or ≥12 years of age as detailed in Table 3 and if clinically indicated. The pregnancy data will be presented in a data listing.

9.7. Vital Signs

Vital signs will be measured at time points per Table 3. Measurements of vital signs will include measurement of pulse, blood pressure (BP), weight, body temperature, and respiratory rate. Pulse and BP in supine or semi-erect/seated position will be measured in each scheduled or unscheduled visits. In addition, standing BP and pulse will be taken at selected visits per Table 3. BMI will be computed similarly as in Section 7.2 at weeks that both weight and height are measured (see Table 3). Normal age and sex-based z-scores, percentiles for BMI, and BMI categories will also be determined using the WHO growth charts similarly as in Section 7.2. Age at the specific visit will be used.

Orthostatic systolic and diastolic BP and pulse will be calculated as supine or semi-erect/seated measurement – standing measurement. Orthostatic hypotension (determined by blood pressure measurements only) is defined as having either a ≥ 20 mmHg reduction from supine to standing position in systolic blood pressure (SBP) or ≥ 10 mmHg reduction from supine to standing position in diastolic blood pressure (DBP) or both. Orthostatic tachycardia is defined as pulse increase ≥ 20 bpm from supine to standing position.

This document is confidential.

Statistical Analysis Plan for Interventional Studies

Sponsor: Teva Branded Pharmaceutical Products R&D, Inc./Nuvelution TS Pharma, INC.
 Protocol No.: TV50717-CNS-30047

Observed values, change from baseline, for each vital sign parameter and position will be summarized at each visit.

In addition, orthostatic hypotension or orthostatic tachycardia occurrences, and the markedly abnormal post-baseline vital signs results will also be summarized for patients with at least one markedly abnormal value during the Parts I and III combined according to criteria specified in [Table 7](#). A listing will be provided for all markedly abnormal vital signs. A shift table for BMI age and set adjusted categories will be presented comparing shifts from the baseline visit to end of treatment. Percentages will be based on the number of patients with a non-missing value for both the baseline and post-baseline visit for the given vital sign.

Table 7: Criteria for Markedly Abnormal Vital Sign Parameters by Age

Parameter (unit)	Age (years old)	Markedly Low	Markedly High
SBP (supine, standing) (mmHg)	6-12	Value ≤ 70 and ≥ 20 decrease from baseline	Value ≥ 120 and ≥ 20 increase from baseline
	13-18	Value ≤ 90 and ≥ 20 decrease from baseline	Value ≥ 135 and ≥ 20 increase from baseline
DBP (supine, standing) (mmHg)	6-12	Value ≤ 40 and ≥ 15 decrease from baseline	Value ≥ 80 and ≥ 15 increase from baseline
	13-18	Value ≤ 50 and ≥ 15 decrease from baseline	Value ≥ 90 and ≥ 15 increase from baseline
Pulse rate (supine, standing) (bpm)	6-10	Value ≤ 60 and ≥ 15 decrease from baseline	Value ≥ 135 and ≥ 15 increase from baseline
	11-18	Value ≤ 50 and ≥ 15 decrease from baseline	Value ≥ 120 and ≥ 15 increase from baseline
SBP orthostatic criteria (mmHg)	~	≥ 20 decrease from supine to standing position	NA
DBP orthostatic criteria (mmHg)	~	≥ 10 decrease from supine to standing position	NA
Pulse rate orthostatic criteria (bpm)	~	NA	≥ 20 increase from supine to standing position
Temperature ($^{\circ}$ C)	~	NA	Value $\geq 38.3^{\circ}$ C and $\geq 0.8^{\circ}$ C increase from baseline

Note: ~ means that the abnormal range is applicable for all patients within age group: 6 to 17 years old.

Vital signs data will be provided in a data listing.

This document is confidential.

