6.2.6. Parts Start and End Dates

For adverse events and concomitant medication, analyses are performed by time period. The following definitions will be used:

- Part I
 - Start Date – the day of the Day 1 visit;
 - End Date - the day of the Week 28 visit, or the day before the Part II first dose date, if patient is dosed during Part II and the Part II first dose date is earlier. If a patient is enrolled but discontinues treatment before the Week 28 visit, Part I is until the last dose of study treatment.
- Part II (The randomized withdrawal period):
 - Start Date - the day after the Week 28 visit, or the Part II first dose date, if it is earlier;
 - End Date the day of the Week 30 visit. If a patient is randomized but discontinues treatment before the Week 30 visit, Part II is until the last dose of study treatment.
- Part III:
 - Start Date - the day after Week 30 visit;
 - End Date - the day of the Week 56 visit. If a patient completed Part II, but discontinues before the Week 56 visit, Part III is until the last dose of study treatment.

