9.8. ECG

Assessment of Standard 12-lead ECG are obtained at visits per [Table 3](#). A central ECG Standard 12-lead ECG will record heart rate (HR), PR interval, RR interval, QT interval, Fridericia's corrected QT interval (QTcF), and QRS duration. The overall ECG assessment will be centrally reported as "Normal" or "Abnormal". If a post-baseline QTcF value >500 msec or change from baseline >60 msec is found, the investigator should repeat the ECG assessment twice. In this case, the confirmed QTcF, defined as the average of all 3 ECG values at the visit, will be used for summary.

Baseline for ECG assessment is the parent study baseline.

Observed results of each ECG parameter and change from baseline will be summarized by visit using descriptive statistics.

In addition, for QTcF, average baseline confirmed QTcF (the average of the parent study screening and baseline QTcF), and the change from average baseline will be summarized visit using descriptive statistics.

QTcF values will be classified as having QTc prolongation according to the following conditions.

QTc Prolongation
Confirmed QTcF >450 msec
Confirmed QTcF >480 msec
Confirmed QTcF >500 msec
Increase from baseline QTcF \geq 60 msec
Increase from average baseline confirmed QTcF \geq 60 msec
Increase from baseline QTcF \geq 30 msec
Increase from average baseline confirmed QTcF \geq 30 msec

The number and percentage of patients with QTc prolongation will be summarized by visit.

A shift table comparing the overall ECG assessment from baseline to each visit will be presented.

In addition, the markedly abnormal post-baseline ECG results will also be summarized for patients with at least one markedly abnormal value during the treatment period. The summary will be completed by the age groups (6 - < 8 years, 8 - < 12 years, and 12 - < 16 years) at the time of the individual assessment.

Criteria for markedly abnormal values used in the study are presented in [Table 8](#).

This document is confidential.

Table 8: Criteria for Abnormal ECG Parameters by Age

ECG parameter (unit)	Age (years old)	Abnormally Low	Abnormally High
HR (bpm)	6 to <8	< 65	> 115
	8 to <12	< 55	> 110
	12 to <16	< 50	> 105
	≥16	< 50	> 100
PR interval (msec)	6 to <8	--	> 160
	8 to <12	--	> 175
	12 to <16	--	> 180
	≥16	--	> 200
QRS interval (msec)	6 to <8	--	> 100
	8 to <12	--	> 105
	12 to <16	--	> 110
	≥16	--	> 120

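### The orthostatic counts (9.7, Table 7) and the HR, PR and QRS abnormality counts (9.8, Table 8) mix findings already present at baseline with new-onset ones

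*SAP*

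**What the plan says.** SAP 9.7 states that "orthostatic hypotension or orthostatic tachycardia occurrences, and the markedly abnormal post-baseline vital signs results will also be summarized" for patients with one or more qualifying values in Parts I and III, using Table 7. The orthostatic rows of that table are "≥ 20 decrease from supine to standing position" for systolic pressure, "≥ 10 decrease from supine to standing position" for diastolic pressure and "≥ 20 increase from supine to standing position" for pulse. The other blood pressure and pulse rows, and the temperature row, pair an absolute limit with a change from the patient's own baseline. The systolic row for ages 6 to 12 is an example: "Value ≤ 70 and ≥ 20 decrease from baseline".

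For ECG, 9.8 states that "the markedly abnormal post-baseline ECG results will also be summarized for patients with at least one markedly abnormal value during the treatment period". The limits in Table 8 are absolute HR, PR and QRS cut-offs by age, with no baseline term. The summary is given by age group. The ECG baseline is the parent study baseline (6.2.1 and 9.8).

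The SAP also plans the following displays that use baseline:
- change from baseline by visit for each vital sign and position;
- change from baseline by visit for each ECG parameter;
- a shift table of the overall Normal/Abnormal ECG reading;
- QTcF increase categories at 30 and 60 msec.

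**The concern.** Long-term safety and tolerability is the primary objective (3.1), and vital signs and ECG are among its endpoints (4.1). A patient with orthostatic tachycardia on Day 1 who shows it again at Week 8 enters the count exactly as does a patient who first shows it at Week 8. The same holds for a long PR interval present at the parent study baseline.

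Elsewhere the SAP uses baseline status. Treatment-emergent events must start or worsen after first dose (9.4), laboratory results get shift tables (9.5), and the C-SSRS gets a shift from baseline to worst category (9.13). Section 4.1 itself describes the ECG endpoint in terms of shifts from the parent study baseline. A reader of the orthostatic and Table 8 counts cannot tell how much of each is new.

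**Working it through.** **Reading check.** For each criterion, does any planned display show whether the flagged patients already met it at baseline?

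| Criterion | Baseline term in the rule | Display split by baseline status |
|---|---|---|
| Table 7, blood pressure, pulse and temperature rows | Yes | Not needed |
| Table 7, three orthostatic rows | No | None; the only shift table in 9.7 is for BMI category |
| Table 8, HR, PR, QRS | No | None; the ECG shift table covers only the overall reading |
| QTcF | Absolute and increase categories | Increase categories cover it |

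By-visit means of change do not identify which flagged patients were positive at baseline. The percentage rule in 9.7 requires a baseline value to exist but does not ask whether it met the criterion. Table 3 has no ECG at Week 30 and does not mark standing measurements there, so Part II offers no randomized comparison on these criteria.

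The baseline data exist. Standing measurements are marked on Day 1 in Table 3, and ECG has the parent study baseline.

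**Size.** The SAP states no figure to reproduce, so this is an illustration on assumed inputs.

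- *k*, the number of post-baseline assessments: 4 for ECG (Weeks 4, 8, 28 and 54 in Table 3). For standing measurements it is 3 or 4: Weeks 4, 8 and 28 are marked, while Week 54 carries a footnote letter that is not the orthostatic one.
- *p*, the background prevalence at one assessment: assumed 5%, range 2% to 10%.
- ρ, the within-patient correlation (ICC): unknown, 0 to 1.
- No drug effect.

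Under a beta-binomial model, a = p(1−ρ)/ρ and b = (1−p)(1−ρ)/ρ. The probability of no qualifying value in m assessments is Q(m) = Π (b+j)/(a+b+j) for j = 0 to m−1. It equals (1−p)^m at ρ = 0 and 1−p at ρ = 1. Then:

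- planned rate = 1 − Q(k);
- negative at baseline and later positive = Q(1) − Q(k+1);
- positive at baseline and counted = planned rate − [Q(1) − Q(k+1)];
- new-onset rate among those at risk = [Q(1) − Q(k+1)] / Q(1).

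Example with p = 0.05, ρ = 0.3, k = 4: a = 0.1167, b = 2.2167, Q(1) = 0.950, Q(4) = 0.8726, Q(5) = 0.8565. The planned rate is 1 − 0.8726 = 12.7%. Negative then positive is 0.950 − 0.8565 = 9.35%. Positive at baseline and counted is 12.7 − 9.35 = 3.4 points. The new-onset rate is 0.0935/0.950 = 9.8%.

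| ρ (p = 5%) | Planned rate, k = 4 | of which positive at baseline | New-onset rate | Planned rate, k = 3 | of which positive at baseline | New-onset rate |
|---|---|---|---|---|---|---|
| 0 | 18.5% | 0.9 points | 18.5% | 14.3% | 0.7 points | 14.3% |
| 0.3 | 12.7% | 3.4 points | 9.8% | 10.8% | 3.0 points | 8.2% |
| 0.6 | 8.9% | 4.3 points | 4.8% | 8.1% | 4.2 points | 4.1% |
| 1 | 5.0% | 5.0 points | 0% | 5.0% | 5.0 points | 0% |

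As a share of the k = 4 count, patients positive at baseline make up 0.9/18.5 = 5%, 3.4/12.7 = 27%, 4.3/8.9 = 48% and 5.0/5.0 = 100%. Applied for illustration to the 157 patients enrolled so far (Table 2), the planned count is about 29 down to 8, of whom about 1 (157 × 0.009) up to 8 (157 × 0.050) were positive at baseline. Over p = 2% to 10% with k = 4, the planned rate spans 2.0% to 34.4% and the new-onset rate 0% to 34.4%.

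**The case against.** Four points on the other side carry weight.

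1. *The orthostatic rule is already a within-patient change, with the supine reading as reference.* That explains why no second difference was added. It does not show whether the patient had the same postural response on Day 1, so the mixing remains.

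2. *Baseline-anchored displays are planned, and vital signs are listed in full.* This stands as mitigation, since group-level change is visible and individual vital signs cases can be traced by hand. The cross-classification for these criteria is still absent.

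3. *These are descriptive counts.* No test, decision or stopping rule depends on them. This stands and limits the weight of the point.

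4. *Table 8 limits change with age, so the same criterion at baseline is undefined for a child who changes age band.* This is a fair point of drafting. Applying the limits for the patient's age at each assessment settles it.

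Two stronger readings are tempting, and the SAP supports neither.

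- A reader might blame the missing baseline condition for the failure of these rates to separate drug effect from background. The cause is mainly the uncontrolled design of Parts I and III. At ρ = 0 the new-onset rate equals the planned rate (18.5%), so intermittent background survives any baseline condition.
- A reader might infer that the baseline reading itself can count as an occurrence, because 6.2.6 starts Part I on "the day of the Day 1 visit". But 6.2.6 confines its dates to adverse events and concomitant medication. The vital signs windows in 6.4 open on Day 2, 6.2.1 makes the last value up to first open-label dose the baseline, and 9.8 expressly limits the ECG summary to post-baseline results.

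**Conclusion.** The point holds as a limited reporting gap. For orthostatic hypotension, orthostatic tachycardia and the HR, PR and QRS limits, the planned counts pool patients who already met the criterion with those who newly met it, and no other planned table separates them.

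The size cannot be fixed from the SAP. On the assumed 5% prevalence with four assessments and no drug effect, 0.9 to 5.0 percentage points of a planned rate of 18.5% to 5.0% come from patients positive at baseline. The more persistent the finding within a patient, the larger that share. The reference differs by measure: Day 1 for orthostatic readings and the parent study baseline for ECG. A new-onset ECG finding may therefore have arisen during the parent study.

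This is a cheap improvement to safety tables that serve the primary objective. It does not invalidate any planned analysis.

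**What to change.** In 9.7 and 9.8, keep the any-occurrence row as planned. For each orthostatic criterion and each Table 8 criterion, add two rows:

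- the number of patients meeting the criterion at baseline;
- a new-onset row. The numerator is patients who did not meet the criterion at baseline and have at least one qualifying post-baseline value. The denominator is patients who did not meet it at baseline and have at least one post-baseline value.

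Use the Day 1 (Part I) baseline for orthostatic measures and the parent study baseline for ECG, and name it in a footnote. Apply the Table 8 limits for the patient's age at each assessment, baseline included. State in the table note that the new-onset rate is not a comparison of drug with background. No threshold changes.

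The cost is one derived flag in the vital signs and ECG datasets and a few lines of SAP text, with no new data. The new-onset denominator is slightly smaller. Persistence in patients positive at baseline shows only in the retained any-occurrence row.
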